10. ASSESSMENT AND MANAGEMENT OF RISK

We do not anticipate significant risks for the participants associated to the study. The main risks are associated with the additional MRI acquired.

MRI is a safe technique and the scans performed in this study will follow routine clinical procedures and using clinical equipment. Patients will be screened by a trained radiographer to ensure that no risks are introduced e.g., metallic objects being brought into the magnetic field of the scanner. Patients will wear earplugs and headphones during the MRI scan to protect from the loud noises generated.

Patients may receive a gadolinium contrast injection which is routinely used in clinical MRI scans of multiple body sites including the kidneys. It is associated with a very low rate of immediate adverse events (0.06-0.09%) and most adverse events are mild e.g., nausea and vomiting. The incidence of acute, severe allergic reactions is estimated to be 0.0025-0.005%(19). Trained medical personnel will always be present to manage this situation. While the patient is in the MRI scanner regular contact will be made between the research team in the control room and the patient. Patients will hold an emergency call button to raise attention or terminate the scan if required.

The scanner software employs a series of safety checks to ensure that any specific set of scan parameters are safe to use. A local institutional quality control procedure is in place locally and will be used to approve any modifications to the pulse sequence software. Specifically, all code modifications are independently checked by two experienced physicists to ensure that:

- All code modifications are fully documented
- All software safety checks are still carried out
- Code modifications do not affect the validity of these software checks
- A risk assessment is produced for each approved set of code modifications to show that the manufacturer's calculations of physiological effects remain valid.

All RFH, UCLH and UCL individuals involved in this study will have received the adequate health and safety training regarding MRI and tissue handling. Therefore, we do not foresee any potential risk given that all protocols are followed accurately. Well established procedures are in place at RFH, UCLH and UCL to cope with the unlikely event of a breach of health and safety protocols.

11.RECORDING AND REPORTING OF ADVERSE EVENTS

11.1 Definitions

Term	Definition
Adverse Event (AE)	Any untoward medical occurrence in a patient or trial participant, which does not necessarily have a causal relationship with the intervention involved.
Serious Adverse Event (SAE).	Any adverse event that: 
• results in death,• is life-threatening*,• requires hospitalisation or prolongation of existing hospitalisation**,• results in persistent or significant disability or incapacity, or• consists of a congenital anomaly or birth defect.• Other 'important medical events' may also be considered serious if they jeopardise the participant or require an intervention to prevent one of the above consequences

* A life-threatening event, this refers to an event in which the participant was at risk of death at the time of the event; it does not refer to an event which hypothetically might have caused death if it were more severe.

** Hospitalisation is defined as an in-patient admission, regardless of length of stay. Hospitalisation for pre-existing conditions, including elective procedures do not constitute an SAE.

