5. TRIAL PROCEDURES

5.1 Pre-MRI renal function testing

Renal impairment with an eGFR <30 ml/min is a relative contraindication to many imaging contrast agents. Renal tests performed in the last 3 months as part of routine standard of care will be used to check renal function.

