11.2.3 Recording of Adverse Events

All adverse events within the first 24 h following an MRI scan will be recorded in the CRF following consent.

Procedures for recording and reporting Serious Adverse Events (SAEs)

All serious adverse events will be recorded in the medical records and the CRF, and the sponsor's SAE log. The CI/PI or designated individual will complete an SAE form and the form will be preferably emailed to the Sponsor within 5 working days of becoming aware of the event. The Chief or Principal Investigator will respond to any SAE queries raised by the sponsor as soon as possible. Where the event is unexpected and thought to be related to the procedure this must be reported by the Investigator to the Health Research Authority within 15 days.

All SAEs will be reported to the Sponsor within 24 hours of becoming aware. The CI/PI or designated individual will complete the Sponsor's online Research Incident Reporting Form (<https://redcap.slms.ucl.ac.uk/surveys/?s=NE5dypTdFo>) within 24 hours of becoming aware of the event. The Chief or Principal Investigator will respond to any SAE queries raised by the Sponsor as soon as possible.

Where the SAE is unexpected and thought to be related to the intervention, this must be reported by the Investigator to the main REC that approved the study within 15 days of the Investigator becoming aware of the event, using the non-CTIMP safety report to REC form. This form can be found on the HRA website: <https://www.hra.nhs.uk/approvals-amendments/managing-your-approval/safety-reporting/>. The Sponsor should be copied into this, so they are aware. Discuss with the JRO Quality Assurance team in the first instance.

Follow-up SAE reports (clearly marked as follow-up) will be completed via <https://redcap.slms.ucl.ac.uk/surveys/?s=NE5dypTdFo> and submitted to the JRO as further information becomes available.

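### The hospitalisation footnote in the SAE definition is not limited to planned admissions or unworsened conditions, so an unplanned admission for worsening renal disease can escape SAE reporting

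*Protocol*

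**What the plan says.** Protocol section 11.1 defines an AE broadly: "Any untoward medical occurrence in a patient or trial participant, which does not necessarily have a causal relationship with the intervention involved". One of the criteria that make an AE serious is that it "requires hospitalisation or prolongation of existing hospitalisation". A footnote attached to that criterion alone first defines the term, "Hospitalisation is defined as an in-patient admission, regardless of length of stay", and then adds the exemption: "Hospitalisation for pre-existing conditions, including elective procedures do not constitute an SAE". The criteria for death, life-threatening events and disability carry no such exemption. Important medical events form a further, discretionary route: they "may also be considered serious if they jeopardise the participant".

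Section 11.2.3 sets two recording duties. For AEs in general: "All adverse events within the first 24 h following an MRI scan will be recorded in the CRF following consent". For serious events, with no stated time limit: "All serious adverse events will be recorded in the medical records and the CRF, and the sponsor's SAE log". The SAE form, the report to the sponsor and, for events both unexpected and related, the report to the REC all depend on SAE status.

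Section 11.2.1 gives special weight to picking up events related to the MRI scan and places the differentiated causality assessment in the SAE form. Appendix 1 lists AE assessment at each scan visit and at end of trial.

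**The concern.** An exemption of this kind normally serves to stop an operation that was already planned from being counted as a safety event. That purpose is legitimate here, because every scanned participant is awaiting resection. The wording goes further. It exempts hospitalisation for pre-existing conditions as a class and gives elective procedures as one included example, so they do not mark its limit.

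In this study the exempted class includes the enrolled disease. Section 4.1 requires a confirmed renal tumour. Section 4.2 excludes only eGFR below 30, so a participant may enter with reduced function above that level. Renal function is also a contrast concern that the protocol itself names: "Renal impairment with an eGFR <30 ml/min is a relative contraindication to many imaging contrast agents". An admission because the tumour or the renal impairment deteriorated after the scan is a mixed event, in which the scan and the underlying condition could both play a part. The category for a possible causal link in section 11.2.1 is written for such events. The footnote can classify the event as non-serious, and the causality assessment on the SAE form is then never made. What is at stake is consistent classification and reporting of such events.

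**Working it through.** No arithmetic decides this point, and the protocol gives no SAE rate to reproduce. The check is to follow an admission through the rules as written.

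**Inputs.** The seriousness criteria and footnote (section 11.1); the eligibility criteria (4.1, 4.2); the assessment and causality rules (11.2, 11.2.1); the recording and reporting rules (11.2.3); the visit schedule (Appendix 1).

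**Scope.** Studies 2 and 3 scan 10 + 10 = 20 participants, over 10 × 1 + 10 × 2 = 30 planned scans. All 20 have a pre-existing renal tumour by eligibility. How many also have reduced renal function is not known in advance.

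| Admission | SAE as written? | Recorded in the CRF? |
|---|---|---|
| Planned nephrectomy, condition not worsened | No, as intended | Not needed as a safety event |
| Unplanned, pre-existing condition worsened, onset within 24 h of MRI, no other criterion met | No | Yes, as an AE; no SAE form |
| The same, onset after 24 h | No | No explicit duty in 11.2.3; only the AE assessments in Appendix 1 |
| Either of the last two, but also fatal, life-threatening or disabling | Yes | Yes, at any time |
| Either of the same two, judged an important medical event | Yes, at discretion | Yes, at any time |
| Admission for a new condition, such as an acute allergic reaction | Yes | Yes, at any time |

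The second and third rows are the problem. A prolonged stay for the same reason follows the same path, since prolongation belongs to the criterion that the footnote qualifies.

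**Within 24 h.** The event reaches the CRF, and section 11.2 requires every AE to be assessed for causality and seriousness. What is lost is SAE status, and with it the SAE form and the SAE report to the sponsor.

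**After 24 h.** SAE status is the only explicit trigger for recording in section 11.2.3, and the footnote removes it. Appendix 1 still lists AE assessment at Visit 2 and end of trial in Study 3, and at end of trial in Study 2. It does not say whether events outside the 24 h window are entered at those points. Section 5.4 sets the end of the study at recruitment of the last patient, so for late recruits the end-of-trial assessment may offer little further follow-up.

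**The case against.** The strongest reply is that the footnote has an evident, sensible purpose: to keep the planned nephrectomy out of the SAE log. An investigator would probably treat a new kidney injury, or a fresh complication, as a new event. A participant with normal renal function has no pre-existing impairment to be exempted. The contrast risks described in section 10 are immediate reactions, none of them a pre-existing condition, and the patients for whom section 5.1 raises the renal concern are excluded. Section 11.5 separately sends incidents that cause injury or ill health to the sponsor and the Trust.

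Much of this stands, and it limits the point. It does not remove it. The text contains no limit to planned or unworsened conditions, so two investigators could classify the same admission differently and both follow the protocol. Section 11.5 concerns unintended or unexpected incidents and does not replace the SAE form or its causality assessment.

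A reader might infer that such an admission can never be an SAE, or that it goes wholly unrecorded. The documents do not support either: the other seriousness criteria still apply, AEs in the first 24 h go in the CRF, and later AE assessments are scheduled. A reader might also infer a specific danger of tumour bleeding after contrast, which the protocol does not name.

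It is also tempting to say that the safety result is biased and to quantify this as a shift in the SAE proportion. The protocol has no safety objective among those in sections 2.1 and 2.2 and plans no estimate of such a proportion. Its only quoted rates are for immediate reactions: 0.06% to 0.09% over at most 30 injections, if every scan includes DCE, gives 30 × 0.0006 = 0.018 to 30 × 0.0009 = 0.027 expected events. That says nothing about late admissions in either direction.

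**Conclusion.** The point holds in a limited form. The footnote in section 11.1 states an exemption wider than its purpose requires. On a literal reading, an unplanned admission or prolonged stay for worsening of the renal tumour or of pre-existing renal impairment is not an SAE when hospitalisation is the only criterion met. The gap in SAE classification and reporting exists at any time after the scan; the gap in explicit CRF recording exists only after 24 h. Both conflict with the importance that section 11.2.1 attaches to scan-related events.

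The REC consequence is narrow, since only SAEs that are both unexpected and related go to the REC. An admission for unrelated disease progression would not be reported there under any wording.

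The reach is all 20 scanned participants, but the number of events affected cannot be estimated from the protocol and may well be zero. The conclusion assumes that staff apply the footnote as written and regard deterioration of the tumour or of existing impairment as hospitalisation for a pre-existing condition. It is a definition that should be corrected. It is not evidence that any event has been or will be missed.

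**What to change.** Replace the exemption sentence in the section 11.1 footnote with wording such as: *An admission planned before consent for a pre-existing condition that has not worsened, including the planned nephrectomy, is not an SAE. An unplanned admission, or a prolonged stay, because a pre-existing condition has worsened since consent is assessed as an SAE.* Carry the same text into the SAE form guidance. At the same time, reconcile section 11.2.3 with Appendix 1, so that it is clear whether AEs found at Study 3 Visit 2 and at end of trial are entered in the CRF when they began more than 24 h after a scan.

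The cost is small: an edit to the footnote, the matching form guidance and a clarifying line. No visits or tests are added. The downside is a few more SAE reports, some unrelated to the scan, because these patients have renal disease and are awaiting surgery, and section 11.2.3 states no end date for SAE recording. The planned nephrectomy stays exempt.

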11.2 Assessments of Adverse Events

Each adverse event (AEs) will be assessed for severity, causality, seriousness and expectedness as described below.

Category	Definition

Mild	The adverse event does not interfere with the participant's daily routine, and does not require further intervention; it causes slight discomfort
Moderate	The adverse event interferes with some aspects of the participant's routine, or requires further intervention, but is not damaging to health; it causes moderate discomfort
Severe	The adverse event results in alteration, discomfort or disability which is clearly damaging to health

11.2.1 Causality

The assessment of relationship of adverse events to the intervention is a clinical decision made by the Investigator (or delegated medically qualified person) based on all available information at the time of the completion of the case report form.

If a differentiated causality assessment which includes other factors in the trial is deemed appropriate, please add/amend the following wording to specify:

It is of particular importance in this trial to capture events related to the MRI scan. The assessment of relationship of an adverse event to this/these additional safety issue(s) will also be carried out as part of the trial.

The differentiated causality assessments will be captured in the study specific SAE form.

The following categories will be used to define the causality of the adverse event:

Category	Definition
Definitely	There is clear evidence to suggest a causal relationship and other possible contributing factors can be ruled out.

Probably	There is evidence to suggest a causal relationship and the influence of other factors is unlikely.
Possibly	There is some evidence to suggest a causal relationship (e.g. the event occurred within a reasonable time after administration of the study procedure). However, the influence of other factors may have contributed to the event (e.g. the participant's clinical condition, other concomitant events).
Related	A causal relationship between the intervention and an adverse event is at least a reasonable possibility, i.e., the relationship cannot be ruled out.
Not related	There is no reasonable possibility of a causal relationship between the intervention and an adverse event.
Not Assessable	Unable to assess on information available.

11.2.2 Expectedness

All SAEs assigned by the Investigator or delegate as suspected to be related to the intervention will be assessed for expectedness against the current SmPC or clearly defined in this protocol.

Category	Definition
Expected	An adverse event which is consistent with the information about the intervention listed in the section 10 of this protocol.
Unexpected	An adverse event which is not consistent with the information about the intervention listed in the MRI instruction manual or clearly defined in this protocol.

* This includes listed events that are more frequently reported or more severe than previously reported.

11.2.3 Recording of Adverse Events

All adverse events within the first 24 h following an MRI scan will be recorded in the CRF following consent.

Procedures for recording and reporting Serious Adverse Events (SAEs)

All serious adverse events will be recorded in the medical records and the CRF, and the sponsor's SAE log. The CI/PI or designated individual will complete an SAE form and the form will be preferably emailed to the Sponsor within 5 working days of becoming aware of the event. The Chief or Principal Investigator will respond to any SAE queries raised by the sponsor as soon as possible. Where the event is unexpected and thought to be related to the procedure this must be reported by the Investigator to the Health Research Authority within 15 days.

All SAEs will be reported to the Sponsor within 24 hours of becoming aware. The CI/PI or designated individual will complete the Sponsor's online Research Incident Reporting Form (<https://redcap.slms.ucl.ac.uk/surveys/?s=NE5dypTdFo>) within 24 hours of becoming aware of the event. The Chief or Principal Investigator will respond to any SAE queries raised by the Sponsor as soon as possible.

Where the SAE is unexpected and thought to be related to the intervention, this must be reported by the Investigator to the main REC that approved the study within 15 days of the Investigator becoming aware of the event, using the non-CTIMP safety report to REC form. This form can be found on the HRA website: <https://www.hra.nhs.uk/approvals-amendments/managing-your-approval/safety-reporting/>. The Sponsor should be copied into this, so they are aware. Discuss with the JRO Quality Assurance team in the first instance.

Follow-up SAE reports (clearly marked as follow-up) will be completed via <https://redcap.slms.ucl.ac.uk/surveys/?s=NE5dypTdFo> and submitted to the JRO as further information becomes available.

11.3 Incidental Findings in Research

In the event that a clinically significant and unexpected finding is found on MRI e.g., unexpected cancer or suspicious lesion, the clinical team will be directly informed by the investigator. In addition, any such findings will be recorded on the standard clinical MRI report on the trust's radiology reporting system.

11.4 Reporting Urgent Safety Measures

If any urgent safety measures are taken the CI/PI shall immediately and in any event no later than 3 days from the date the measures are taken, give written notice in the form of a substantial amendment to the relevant REC and Sponsor of the measures taken and the circumstances giving rise to those measures.

11.5 NHS Serious Incidents and Near Misses

A serious incident or near miss is any unintended or unexpected event that could have or did lead to harm, loss or damage that contains one or more of the following components:

- a. It is an accident or other incident which results in injury or ill health.
- b. It is contrary to specified or expected standard of patient care or service.
- c. It places patients, staff members, visitors, contractors or members of the public at unnecessary risk.
- d. It puts the Trust in an adverse position with potential loss of reputation.
- e. It puts Trust property or assets in an adverse position or at risk.

Serious Incidents and near misses will be reported to the Sponsor and Trust Quality & Safety department as soon as the study team becomes aware of them.

11.6 Complaints from research participants

In the first instance, research participant complaints (patients or health volunteers) will be reported to the CI/PI to investigate, as documented in the patient information sheet(s), and to the Sponsor via [contact], following the *UCL Complaints from Research Subjects about UCL Sponsored Studies and Trials* policy. For participants who are NHS patients, complaints will be reported to the NHS Complaints Manager at the Trust where the recruitment and study procedures were undertaken. Complaints from NHS patients are handled under NHS complaints policies and procedures, with involvement from PALS and the Sponsor where necessary.

12. REGULATORY REVIEW AND PATIENT AND PUBLIC INVOLVEMENT

12.1 Regulatory Review

The Sponsor will ensure that the trial protocol, participant information sheet, consent form, GP letter and submitted supporting documents have been approved by the appropriate research ethics committee, prior to any participant recruitment. The protocol, all other supporting documents including and agreed amendments, will be documented and submitted for ethical and regulatory approval as required. Amendments will not be implemented prior to receipt of the required approval(s).

The study was deemed to require regulatory approval from the following bodies NHS REC Favourable Opinion and HRA Approval). **Before any site can enrol patients into the study**, the Chief Investigator/Principal Investigator or designee will ensure that the appropriate regulatory approvals have been issued, and NHS Confirmations of Capacity and Capability and Sponsor green lights are in place.

For any amendments to the study, the Chief Investigator or designee, in agreement with the Sponsor, will submit information to the appropriate body in order for them to issue approval for the amendment. The Chief Investigator or designee will work with sites (R&D departments as well as the study delivery team) to confirm ongoing Capacity and Capability for the study.

All correspondence with the Sponsor, REC and HRA will be retained. The Chief Investigator will notify the Sponsor and REC of the end of the study.

It is the Chief Investigator's responsibility to produce the annual progress reports when required; an annual progress report (APR) will be submitted to the Sponsor and REC within 30 days of the anniversary date on which the favourable opinion was issued, and annually until the study is declared ended.

Within 90 days after the end of the trial, the CI will ensure that the main REC is notified that the trial has finished. If the trial is terminated prematurely, those reports will be made within 15 days after the end of the trial.

Within one year after the end of the study, the Chief Investigator will submit a final report with the results, including any publications/abstracts, to the Sponsor and to the REC and HRA.

